3.7 Center pooling strategy

Geographic regions have been categorized as North America, Western Europe, Central/Eastern Europe, and Asia/Australia. Below is a table of geographic regions with corresponding countries.

Table 3–1: Geographic regions and corresponding countries

Region	Countries
North America	Canada, United States

Table 3–1: Geographic regions and corresponding countries

Region	Countries
Western Europe	France, Germany, Ireland, Italy, Spain, United Kingdom
Central/Eastern Europe	Bulgaria, Czech Republic, Hungary, Poland
Asia/Australia	Australia, Israel, Japan

The following center pooling algorithm will be used for each geographic region:

- If a center has 21 or more participants, then no pooling will be done for that center.
- Centers with fewer than 21 participants will be ordered from largest to smallest with pooling proceeding in the following manner:
 - Two or more centers will be combined until the cumulative participant total is at least 21.
 - Once a pooled center has at least 21 participants, the process will continue in an iterative fashion for the subsequent centers in the ordered list, where a new pooled center begins each time at least 21 participants has been reached in the previous pool.
 - If this iterative process reaches the end of the ordered list of centers where the final pooled center has fewer than 21 participants, then the participants from the centers in that pool will be combined with the pooled center formed in the previous iteration.

This procedure is only to be performed within a geographic region – there will be no pooling of centers across regions.

In the event that the percentage of randomized participants is less than 10% in either of the Asia/Australia or Central/Eastern Europe regions, the two regions will be combined as a geographic region stratum for efficacy modeling, so that there are no modeling convergence issues across efficacy variables.

3.8 Coding dictionaries

Adverse events and medical history will be coded using the Medical Dictionary for Regulatory Activities (MedDRA®) version 19.0.

Medications will be coded according to the World Health Organization Drug Dictionary (WHODD) version MAR2021 B3 or later. Medical procedures will not be coded.

3.9 Definition of an intercurrent event

Handling of intercurrent events is one of the key elements for the analysis of efficacy endpoints.

An intercurrent event is defined as receipt of systemic antibiotic rescue medication or discontinuation of study treatment due to an AE or lack of efficacy (See Section 8.2.2).

Receipt of systemic antibiotic rescue medication is defined as initiating any systemic antibiotic on or after Baseline for any reason (including in response to an AE). The only exception to this rule is if a participant randomized to the antibiotic stratum on a tetracycline antibiotic interrupts

their stable dose of tetracycline antibiotic during the study and subsequently restarts the same tetracycline antibiotic as confirmed using the coded preferred term. The restarted dose and frequency of the antibiotic must be the same or lower than the regimen prior to the interruption.

The dates of an intercurrent event are as follows:

- For receipt of systemic antibiotic rescue medication: start date of the antibiotic
- For discontinuation of study treatment due to an AE or lack of efficacy: Last study treatment date + 17 days. Note: study treatment discontinuation includes study discontinuation.

The choice of 17 days is intended to capture the interval between dosing and lesion assessments (14 days), as well as the visit window (3 days).

An additional sensitivity analysis will be conducted where missing data due to COVID-19 will be considered an intercurrent event and will be imputed as a nonresponse at that particular visit. This will be identified when there are missing data at a visit that has been impacted by COVID-19 according to the COVID-19 impact CRF page. The date of this intercurrent event will be the date of the impacted visit.

3.10 Changes to protocol-defined analyses

The MS and AMS were added as analysis sets.

The endpoints for PGI-S-HS, PGI-S-SP, PGI-C-HS, and PGI-C-SP were clarified in Section 2.2.1.3 to indicate that absolute change from Baseline will not be calculated, as these are categorical endpoints.

The HiSQOL endpoint was clarified to show that there are only 3 domains: symptoms, psychosocial, activities and adaptations and to add total score.

In Protocol Amendment 4, the secondary efficacy endpoint for skin pain response based on the worst skin pain HSSDD score is defined as a decrease from Baseline in HSSDD weekly worst skin pain score at or beyond the threshold for clinically meaningful change at Week 16. In this SAP, this endpoint is defined to include the exact value of the clinically meaningful threshold of 3, so that the skin pain response based on the HSSDD worst skin pain score is defined as at least a 3 point decrease from Baseline in HSSDD weekly worst skin pain score at Week 16 among study participants with a score of ≥ 3 at Baseline.

The following other efficacy endpoints are included in the protocol but will not be included as part of the analysis:

- Skin pain response based on the threshold for clinically meaningful change (defined as at least a 3 point decrease from Baseline in HS Symptom Questionnaire (HSSQ) weekly worst skin pain score) among study participants with a score of ≥ 3 at Baseline
- Response on other HS Symptoms (11-point numeric rating scale) - itch, drainage or oozing of HS lesions, and smell or odor
- Flare (defined as a $\geq 25\%$ increase in AN count with an absolute increase in AN count of ≥ 2 relative to Week 16) by Week 48

The calculation of nominal p-values has been added for selected efficacy endpoints. These nominal p-values are not controlled for multiplicity and should not be used to declare statistical significance.

The protocol defines the PK-PPS separately by period, but there will only be one PK-PPS for the overall study.

4 STATISTICAL/ANALYTICAL ISSUES

4.1 Adjustments for covariates

The primary efficacy analyses and selected secondary analyses will be adjusted for the 2 randomization stratification variables:

- Hurley Stage at Baseline (II or III)
- Baseline antibiotic use (Yes or No)

If a participant is stratified in the incorrect stratum (ie, the stratum recorded in the Interactive voice or web Response System differs from the actual stratum the participant belongs to), the actual stratum will be used for the analysis.

The continuous secondary endpoints will also include the Baseline value as a covariate.

The Worst Skin Pain secondary endpoints (change from Baseline continuous endpoint and pain response binary endpoint) will also include analgesic use as a covariate.

4.2 Handling of dropouts or missing data

4.2.1 Efficacy data

Different approaches will be used to handle missing data including how intercurrent events (defined as receipt of systemic antibiotic rescue medication or discontinuation of study treatment due to an AE or lack of efficacy prior to the given visit) will be considered. A composite strategy will be implemented in which a positive clinical outcome is defined as the study participant achieving HiSCR₅₀ at the given visit and not receiving systemic antibiotic rescue medication, and not discontinuing study treatment due to an AE or lack of efficacy through that visit.

4.2.1.1 Handling missing data for the primary efficacy endpoint

If study participants have an intercurrent event as defined in Section 3.9, then the primary efficacy variable at that timepoint and all subsequent timepoints (whether the data were observed or not) will be set to “nonresponse” as the study participant has not met the criteria for response based on the composite estimand defined in Section 8.2. All remaining missing data for the endpoint will be imputed using multiple imputation Markov-Chain Monte Carlo method (MI-MCMC)/monotone regression for the primary analysis.

In addition, sensitivity analyses using NRI, MI-MCMC/reference-based methods, tipping point analysis, and observed case (OC) methods will be performed, which will assess the impact of different methods of handling missing data.

4.2.1.2 Handling missing data for the secondary efficacy endpoints

For secondary binary efficacy endpoints, intercurrent events will be handled, and missing data will be imputed, using the same methods as for the primary efficacy endpoint. NRI and OC methods will be performed as sensitivity analyses.

For secondary continuous efficacy endpoints, MI-MCMC/monotone regression is the primary method for imputing missing data, regardless of whether the missing data are preceded by an intercurrent event. That is, if an intercurrent event occurs on or before a visit, the result for that visit will be treated as missing and then imputed. If the imputation model cannot converge, last observation carried forward (LOCF) will be used. The OC method will be performed as a sensitivity analysis.

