4.2.1.4 Missing Data Overview and Summary

In summary, the approaches listed below will be used in this study for handling missing data for efficacy endpoints as appropriate:

- **NRI:** Participants who have missing data at the timepoint of interest are treated as though they did not respond to the treatment. This approach is also referred to as Composite Estimand (NRI).
- **Multiple Imputation (MI) – MCMC / Monotone Regression:** Using multiple imputation methodology, intermittent missing data are imputed based on the MCMC method, and monotone missing data are imputed using monotone regression.
- **MI–MCMC / Reference-based imputation:** Using multiple imputation methodology, intermittent missing data are imputed based on the MCMC method, and monotone missing data are imputed using an imputation model based on placebo (reference) data.
- **LOCF:** Post-Baseline missing data are imputed by carrying forward the last available observation (including Baseline).
- **Tipping point analyses:** Assumptions will be made about average outcomes among the subsets of participants who prematurely discontinued study treatment. Various “delta adjustments” will be made to the assumed responses among missing data in each treatment arm with varying degrees of plausibility in order to identify assumptions about the missing

data under which the conclusions change (O’Kelly, 2014). Then, the plausibility of such assumptions is discussed.

- **Observed case (OC):** Missing data are not imputed. Only participants with available data who have not discontinued study treatment at the given timepoint are considered. Study participants with missing data or who have prematurely discontinued study treatment will be treated as missing.

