For hs-CRP only, the following rules apply. The hs-CRP data will be presented using the geometric mean, 95% CI for the geometric mean, median, Q1, Q3, minimum and maximum. The change from Baseline will be expressed as the ratio to Baseline in the summaries. The following approach will be applied:

- Following the MI procedure, the ratio to Baseline will be calculated for any of the imputed values
- The natural logarithm of the absolute values and of the ratios to Baseline will be calculated
- The logged values will be summarized (using PROC MEANS) by treatment, visit and imputation
- The datasets will be combined using PROC MIANALYZE in order to get the mean and 95% CI estimates from the absolute values and ratios to Baseline (based on logged data) across imputations
- The estimates of the mean and 95% CI will be back-transformed to obtain the geometric mean and 95% CI on the original scale
- For the median, Q1, Q3, minimum and maximum the procedure outlined above for the other endpoints will be followed

If the imputation model cannot converge, LOCF will be used.

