4.5 Multiple comparisons/multiplicity

To control the overall type I error rate at 0.05 for the multiple comparisons in the primary and secondary efficacy endpoints, a closed testing procedure under a parallel gatekeeping framework will be applied (Sun, 2018).

[figure not shown]
Under this framework, each bimekizumab dose of [REDACTED] and [REDACTED] will be compared to placebo in the first instance at a familywise error rate of 0.025 ($\alpha/2$). Simultaneously within each dose, closed testing for the primary and secondary efficacy endpoints will be performed as follows:

1. Step 1: Test HiSCR₅₀ at significance level 0.025.
2. Steps 2 to 6 – If Step 1 is significant at 0.025 then test each secondary endpoint sequentially in the order shown in Figure 4-1, moving to the next step only if significance achieved at 0.025.
3. In the event that Step 6 is significant at 0.025 for a given dose, then Steps 1 to 6 will be repeated for the other dose using a significance level of 0.05.

The secondary efficacy variables supporting the primary efficacy variable are listed below, and will be included in the multiplicity adjustment using the analysis methods specified in Section 8.3:

1. Proportion of study participants who achieve HiSCR₇₅ at Week 16.
 - a. bimekizumab [REDACTED] vs placebo
 - b. bimekizumab [REDACTED] vs placebo
2. Proportion of study participants who experience at least 1 flare by Week 16, with flare defined as a $\geq 25\%$ increase in AN count with an absolute increase in AN count of ≥ 2 relative to Baseline.
 - a. bimekizumab [REDACTED] vs placebo
 - b. bimekizumab [REDACTED] vs placebo
3. Absolute CFB in DLQI Total Score at Week 16.
 - a. bimekizumab [REDACTED] vs placebo
 - b. bimekizumab [REDACTED] vs placebo
4. Absolute CFB in Skin Pain Score at Week 16, as assessed by the “worst skin pain” item (11-point numeric rating scale) in the HSSDD.
 - a. bimekizumab [REDACTED] vs placebo
 - b. bimekizumab [REDACTED] vs placebo
5. Skin pain response at Week 16, based on the threshold for clinically meaningful change (defined as at least a 3 point decrease from Baseline in HSSDD weekly worst skin pain score) at Week 16 among study participants with a score of ≥ 3 at Baseline.
 - a. bimekizumab [REDACTED] vs placebo
 - b. bimekizumab [REDACTED] vs placebo

Figure 4-1: Sequence of testing

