8.3 Secondary efficacy endpoints

The secondary efficacy analyses will be performed based on the RS. Sensitivity analyses of the secondary endpoints will be performed on the CFS.

Missing data handling and sensitivity analyses of the secondary efficacy endpoints are described in Section 4.2.1.2.

The analyses of the secondary endpoints are summarized in Table 8–2 .

Table 8–2: Estimand Details and Attributes for Secondary Analyses

Objective Clinical Category	Statistical Category (Section)	Estimands for Secondary Endpoints			PLS (Analysis)
		Variable/Endpoint	Pop	IES	
Secondary Objective: Evaluate the efficacy of bimekizumab on other measures of disease activity in study participants with moderate to severe HS					
HiSCR ₇₅	Secondary (Section 8.3.1)	HiSCR ₇₅ response at Week 16	RS	Composite strategy, as for the primary analysis.	The odds ratio versus placebo based on a logistic regression, as for the primary analysis.

Table 8–2: Estimand Details and Attributes for Secondary Analyses

Objective Clinical Category	Statistical Category (Section)	Estimands for Secondary Endpoints			PLS (Analysis)
		Variable/Endpoint	Pop	IES	
Flare	Secondary (Section 8.3.2)	Flare by Week 16	RS	The main intercurrent events are receipt of systemic antibiotic rescue medication or discontinuation of study treatment due to an AE or lack of efficacy prior to Week 16. A composite strategy will be used, ie, the occurrence of an intercurrent event will be handled by evaluating the corresponding participants as treatment failures (flare).	The odds ratio versus placebo based on a logistic regression, as for the primary analysis.
DLQI	Secondary (Section 8.3.3.1)	Change from Baseline in DLQI total score to Week 16	RS	The main intercurrent events are receipt of systemic antibiotic rescue medication or discontinuation of study treatment due to an AE or lack of efficacy prior to Week 16. The intercurrent events will be handled using a hypothetical strategy , whereby all data at and after the intercurrent event will be treated as missing.	Difference in mean change from Baseline (LSMD from ANCOVA) to Week 16 in the DLQI total score for participants receiving bimekizumab versus placebo. Missing values will be imputed using MI – MCMC/Monotone Regression under a missing at random assumption.

Table 8–2: Estimand Details and Attributes for Secondary Analyses

Objective Clinical Category	Statistical Category (Section)	Estimands for Secondary Endpoints			PLS (Analysis)
		Variable/Endpoint	Pop	IES	

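### LOCF is the fallback for two alpha-controlled continuous endpoints, and the SAP does not require its own milder imputation remedies first

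*SAP*

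**What the plan says.** For the secondary continuous endpoints, Section 4.2.1.2 states that "MI-MCMC/monotone regression is the primary method for imputing missing data, regardless of whether the missing data are preceded by an intercurrent event". It then adds that, if the imputation model does not converge, "last observation carried forward (LOCF) will be used". The continuous-endpoint part of Section 4.2.2.1 closes with the same rule: "If the imputation model cannot converge, LOCF will be used". By the definition in Section 4.2.1.4, the carried value may be the Baseline value, which gives a change of exactly zero.

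The rule reaches two endpoints. Sections 8.3.3.1 (DLQI) and 8.3.4 (worst skin pain) both send missing data to Section 4.2.1.2. Both are tested under Section 4.5: "Absolute CFB in DLQI Total Score at Week 16" is Step 4, and the worst skin pain change is Step 5 of six. For both, Table 8-2 sets a hypothetical strategy, "whereby all data at and after the intercurrent event will be treated as missing", and then: "Missing values will be imputed using MI – MCMC/Monotone Regression under a missing at random assumption". LOCF appears in neither Table 4-1 nor Table 8-2.

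Section 4.2.2.1 also permits less drastic steps. Baseline antibiotic use, and then Hurley Stage, may be dropped from the imputation model. If there are computational problems, one model with treatment as a variable may replace the separate models per arm.

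**The concern.** Multiple imputation under missing at random predicts the Week 16 value from a participant's earlier values, given how others in the same arm went on. LOCF assumes that the participant stays exactly where last seen, or at Baseline. Where means are still moving with time, or dropout differs between arms, the two assumptions give different treatment differences. LOCF also adds no between-imputation variance, although Section 4.2.2.1 relies on Rubin's rules to carry it.

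The wording leaves the trigger loose. The milder steps are permitted, not required, and nothing places them before LOCF. Imputation runs arm by arm by default, yet the SAP does not say whether a failure in one arm would bring in LOCF for that arm only or for all.

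At stake are Steps 4 and 5 of the sequence. They decide whether Step 6 is reached, and so whether the other dose is retested at 0.05. The pain change is the more exposed: Section 2.4 says that it drives the sample size, with 73% power at 0.025 for the 140:70 comparison.

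**Working it through.** **The SAP's own figures.** Table 2-1 inputs for pain, 140:70: mean changes -2.0 and -0.5, SDs 3.2 and 3.7.

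- SE of the difference = sqrt(3.2²/140 + 3.7²/70) = sqrt(0.0731 + 0.1956) = 0.518; 1.5/0.518 = 2.89.
- A Welch t-test (noncentral t) gives power 0.733 at two-sided 0.025 (stated 0.73) and 0.819 at 0.05 (stated 0.81).
- Pain at 280:70 gives 0.893 (stated 0.89). DLQI gives 0.966 and 0.998 (stated 0.96 and 0.99).

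The planning figures are sound.

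**LOCF against multiple imputation.** The SAP gives no missing-data rate, so this part is illustrative. Inputs from Table 2-1: means, SDs and 140:70, hence true differences of -1.5 (pain) and -4.0 (DLQI). Assumptions not in the SAP: four visits; AR(1) correlation 0.7; 50, 75, 90 and 100% of the effect reached by visit; dropout of 10 or 25% per arm, either completely at random (MCAR) or at random given earlier values (MAR); 200 replicates; 10 imputations with Rubin's rules. Full means the same simulated data before dropout.

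| Endpoint | Dropout, bimekizumab/placebo | Full | LOCF | MI | SE LOCF | SE MI | SE ratio |
|---|---|---|---|---|---|---|---|
| Pain | 10/10 MCAR | -1.506 | -1.479 | -1.518 | 0.518 | 0.544 | 0.95 |
| Pain | 10/10 MAR | -1.448 | -1.418 | -1.430 | 0.529 | 0.543 | 0.97 |
| Pain | 10/25 MCAR | -1.472 | -1.464 | -1.481 | 0.517 | 0.572 | 0.90 |
| Pain | 10/25 MAR | -1.482 | -1.691 | -1.477 | 0.540 | 0.589 | 0.92 |
| Pain | 25/10 MCAR | -1.501 | -1.386 | -1.504 | 0.518 | 0.556 | 0.93 |
| Pain | 25/10 MAR | -1.498 | -1.208 | -1.486 | 0.536 | 0.558 | 0.96 |
| DLQI | 10/10 MCAR | -4.014 | -3.894 | -3.997 | 0.978 | 1.029 | 0.95 |
| DLQI | 10/10 MAR | -4.035 | -3.873 | -4.002 | 1.006 | 1.029 | 0.98 |
| DLQI | 10/25 MCAR | -4.020 | -3.890 | -3.982 | 0.974 | 1.080 | 0.90 |
| DLQI | 10/25 MAR | -3.931 | -4.221 | -3.947 | 1.019 | 1.096 | 0.93 |
| DLQI | 25/10 MCAR | -3.984 | -3.685 | -4.002 | 0.980 | 1.057 | 0.93 |
| DLQI | 25/10 MAR | -3.912 | -3.184 | -3.896 | 1.010 | 1.054 | 0.96 |

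- **Bias.** Under MAR, LOCF moves the pain difference away from the full-data value by 0.29 toward zero (25/10) or by 0.21 away from zero (10/25). For DLQI the shifts are 0.73 toward zero and 0.29 away. MI stays within 0.04 of full data in every row.
- **Standard errors.** LOCF is 2 to 10% below MI. Its reported SE is, however, 0.94 to 1.06 times its own sampling SD (for example 0.536 against 0.573 for pain 25/10 MAR, and 1.019 against 0.961 for DLQI 10/25 MAR).
- **Consequence for the test.** Mean estimate over mean SE, against the SAP's critical value of 2.24. Pain 25/10 MAR: LOCF 1.208/0.536 = 2.25, MI 1.486/0.558 = 2.66. Pain 10/25 MAR: LOCF 1.691/0.540 = 3.13, MI 1.477/0.589 = 2.51. For DLQI the lowest LOCF value among the MAR rows is 3.184/1.010 = 3.15. In this simulation the pain test is the one whose outcome could turn on the method.

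**The case against.** The strongest reply is that this concerns a remote contingency. The planned analysis is multiple imputation. Covariates can be dropped and arms pooled. The difficulty that Section 4.2.2.1 gives as its example, a zero standard deviation, is hard to imagine for a 0 to 30 total or a non-integer 0 to 10 weekly average in groups of at least 70. The monotone step is sequential regression, so convergence matters mainly for the MCMC step that fills intermittent gaps. All of this stands. It makes the point minor, but it does not order the remedies.

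Second, an observed-case ANCOVA is prespecified for both endpoints and would be reported beside any LOCF result. That is true, but it is a sensitivity analysis and the LOCF result would still decide the test.

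Third, a mixed model with an unstructured covariance estimates much the same covariance matrix as MCMC and could fail on the same data. This is fair, and it is why the fix must fix a sequence of covariance structures.

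Fourth, a reader might infer that LOCF would understate its own error. The simulation does not support that: the reported SE was close to LOCF's sampling SD. Only the comparison with MI holds.

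Fifth, a reader might infer that the estimand itself changes. Post-event data are set aside either way and the hypothetical strategy in Table 8-2 stays in place. What changes is the assumption used to fill the gap.

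**Conclusion.** The point holds as a cheap improvement, not as an error in the planned analysis. As written, a confirmatory test of DLQI or of worst skin pain change could move from missing at random to a constant-profile single imputation before the SAP's own milder remedies have been used. The chance is low.

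If it happened, the illustrative LOCF estimates run from -1.21 to -1.69 for pain (true -1.5) and from -3.18 to -4.22 for DLQI (true -4.0), with SEs 2 to 10% below those of MI. These sizes rest on assumed dropout, correlation and time course.

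Two further inferences are not supported. LOCF does not systematically favor bimekizumab: the direction depends on which arm loses more participants and on why. With 10/25 dropout it exaggerated both differences under MAR but not under MCAR. Nor is the binary skin pain response affected: Section 4.2.1.2 gives it the primary endpoint's methods, with no LOCF fallback.

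**What to change.** For DLQI change and worst skin pain change, replace the LOCF sentence in Sections 4.2.1.2 and 4.2.2.1 with a mandatory order, each step used only if the one before fails:

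1. Drop Baseline antibiotic use, then Hurley Stage, from the imputation model (already permitted).
2. Fit one imputation model across arms with a treatment term (already permitted).
3. Add a ridge prior to the MCMC step.
4. Fit a mixed model for repeated measures to pre-event data under missing at random, with the covariates of the planned ANCOVA (including analgesic use for pain), treatment-by-visit, and a prespecified sequence of covariance structures: unstructured first, then simpler ones.

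State that a step, once needed, applies to all arms. Keep LOCF at most as a supportive analysis. The cost is a short text change and a back-up program that will probably never run.
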